5.5 Medications/Procedures

At each study visit, investigators will review concomitant medications and procedures with the patients. The World Health Organization (WHO) Drug Dictionary March 2018 will be used to classify medications by preferred term, chemical ingredient names and WHO Level 3 Anatomical Therapeutic Chemical (ATC) classification of trade name. Medication records will be characterized as prior medication and/or concomitant medication based on the subjects' start and end date of the study drug.

5.4.1 Prior Medications/Procedures

Prior medications/procedures are defined as any medications/procedures started and ended before the first dose of the study drug.

5.4.2 Concomitant Medications/Procedures

Any medications/procedures that begin before the start of the first dose of study drug and continue past that, or that begins on or after the first dose of study drug and up to 28 days post the date of the last dose of the DB medications will be considered as concomitant medications/procedures.

6. STATISTICAL METHODOLOGY

Titles and headers of all statistical analysis tables will indicate the corresponding study population; the number of subjects for the population and for each treatment will be presented in the tables. Summary statistics for continuous parameters will include the number of subjects (N), mean, standard deviation (SD), median, minimum and maximum. For plasma concentrations, summary statistics will also include the coefficient of variation (CV%). Summary statistics for discrete parameters will include frequency count and percentage of which the denominator will be clearly indicated in the analysis table.

For efficacy and safety summaries, mean and median will be presented to 1 more decimal than the source data; SD will be presented to 2 more decimals than the source data; minimum and maximum will be presented in the same precision as the source data. Percentages including response rate will be presented to 1 decimal, e.g., xx.x%. P-values will be presented to 3 decimals. P-values greater than 0.999 will be presented as >0.999; p-values less than 0.001 will be presented as <0.001.

For figures, the corresponding study population will be included in the titles. All collected observations will be included in the related listings.

Baseline value is defined as the last non-missing value prior to the first dose.

For the safety and efficacy analyses, only assessments from scheduled visits will be used for summary tables, however, data collected from both scheduled and unscheduled visits will appear in the subject listings.

When calculating percent change from baseline in efficacy analyses, measures scored as 0 at baseline will be managed as missing values when they did not change from 0, and as 0% change when they were increased (i.e., worsened).

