3.4. Removal of Subjects from the Study

[figure not shown]
A subject will not participate further in the study under the following conditions:

1. Withdrawal by Subject: subjects have the right to withdraw from the study at any time. However, if a subject withdraws consent because of experiencing an adverse event, the reason for subject termination should be documented as the adverse event.
2. Adverse Event: a clinical or biological adverse event or intercurrent condition(s), requiring study drug discontinuation, whether or not related to the study drug

If grade 3 findings (defined as severe or medically significant but not immediately life-threatening; hospitalization or prolongation of hospitalization indicated; disabling; limiting self-care activities of daily living [ADL] such as bathing, dressing, undressing, feeding self, using the toilet, taking medication, but not bedridden), according to the CTCAE²⁵, are noted in a subject, he/she must be promptly evaluated by the Investigator (including repeat tests, evaluation of the baseline parameters, concomitant medications, etc.) for potential withdrawal from the study. Every effort should be made to discuss with the study's Medical Monitor prior to final decision, unless not feasible, based on safety considerations. Subjects who interrupted study drug administration due to a grade 3 CTCAE finding may be re-started on therapy if the event has resolved and it is considered appropriate by the Investigator and Sponsor or designee.

Notes:

- The investigator may decide to evaluate or withdraw the subject from the study based on findings of lesser than grade 3 severity, according to his/her judgment.

3. Consistent* Non-compliance with Study Drug (i.e., <80% or >120% compliance; exceptions on a case-by-case basis may be permitted if approved by Sponsor or designee)

*Determined at >1 study visit during the Treatment Period. If compliance of <80% or >120% is identified at a study visit, the Investigator or designee is to counsel the subject and ensure steps are taken to improve compliance.

4. Inclusion/Exclusion Criteria Not Met: the subject was randomized in the study and did not meet all inclusion/exclusion criteria mandated by the protocol (exceptions on a case-by-case basis may be permitted if approved by Sponsor or designee)

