5.3.6 Clinical Laboratory Results

Hematology, coagulation, serum biochemistry, bone-specific alkaline phosphatase, lipid profile and urinalysis are collected as scheduled in [Table 1](#). The following information will be

derived for each of the hematology, coagulation, serum biochemistry, urinalysis and other parameters:

- Change from baseline at all post-baseline visits
- Classification relative to the normal range ('Low', 'Normal' or 'High')
- Treatment-Emergent potentially clinically significant (PCS) abnormalities, if applicable

Abnormalities in liver tests will be identified.

In addition, 25-hydroxyvitamin D, rheumatoid factor (RF), anti-cyclic citrullinated peptide (anti-CCP) antibodies and serum immunoglobulins G, M and A (IgG, IgM and IgA), viral serology, drugs of abuse and alcohol screen, pregnancy test and follicle stimulating hormone will also be obtained at the corresponding scheduled visit, respectively.

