6.5 Safety Analysis

All safety analysis will be performed on the Safety population.

Potentially clinically significant (PCS) abnormalities will be defined according to the Akros Safety Reporting Standards (Standard72.doc, 10/18/2004). The PCS values for vital signs, ECG and laboratory data will be flagged in data listings.

Treatment-emergent PCS values will be summarized, presenting the number and percentage of subjects who had at least one PCS value on or after the first dose of study drug (JTE-051 or

placebo). The denominator is always the number of subjects in the safety population, regardless of whether the subject had any post-baseline measurements. The numerator is any PCS value in the treatment-emergent period if the baseline is normal or missing; and is any worsening PCS value in the treatment-emergent period if the baseline is also a PCS value. A worsening PCS is defined as a $> (<)$ 0 change from baseline if a high (low) value indicating undesirable outcome; or the PCS value is in the opposite direction of the baseline PCS value. Note that for the purpose of determining PCS abnormalities, baseline is always the last non-missing value before the first dose of study drug.

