6.5.3 Clinical Laboratory Tests

Descriptive statistics of observed results and change from baseline for hematology, coagulation, serum biochemistry, bone-specific alkaline phosphatase, lipid panel and continuous urinalysis will be presented by time point and treatment group. Frequency and percentage of the distribution of discrete urinalysis tests will be presented by time point. Number and percentage of subjects with treatment-emergent PCS abnormal values will be summarized by treatment group.

Number and percentage of subjects with post-baseline abnormalities in liver tests will be summarized by treatment group according to [Table 3](#).

Table 3. Criteria for Categorical Analysis in Liver Tests

Parameter	Specified Value			
ALT	ALT \geq ULN \times 3	ALT \geq ULN \times 5	ALT \geq ULN \times 10	ALT \geq ULN \times 20
AST	AST \geq ULN \times 3	AST \geq ULN \times 5	AST \geq ULN \times 10	AST \geq ULN \times 20
ALT and AST	ALT and AST \geq ULN \times 3	ALT and AST \geq ULN \times 5	ALT and AST \geq ULN \times 10	ALT and AST \geq ULN \times 20
ALT or AST	ALT or AST \geq ULN \times 3	ALT or AST \geq ULN \times 5	ALT or AST \geq ULN \times 10	ALT or AST \geq ULN \times 20
T-Bil	T-Bil $>$ ULN \times 1.5		T-Bil $>$ ULN \times 2	
ALP	ALP $>$ ULN \times 1.5			
ALT and T-Bil	ALT \geq ULN \times 3 and T-Bil \geq ULN \times 1.5		ALT \geq ULN \times 3 and T-Bil \geq ULN \times 2	
AST and T-Bil	AST \geq ULN \times 3 and T-Bil \geq ULN \times 1.5		AST \geq ULN \times 3 and T-Bil \geq ULN \times 2	
AT, ALP and T-Bil	ALT \geq ULN \times 3, AST \geq ULN \times 3, ALP \geq ULN \times 2 and T-Bil \geq ULN \times 2			
ALT and AST	ALT or AST $>$ ULN \times 3 at any treatment visit and any of the following AEs: Nausea, Vomiting, Anorexia, Abdominal pain or Fatigue, reported within +/- 14 days of the abnormal AT values.			

Other clinical laboratory tests (e.g., drug abuse, alcohol screen, viral serology) will be listed in the data listings.

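### The scheduled-visit rule in SAP 6 has no exception for the subject-level PCS and liver counts, so a value reached only at an unscheduled draw is not counted

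*SAP*

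**What the plan says.** SAP 6 sets one general rule: "For the safety and efficacy analyses, only assessments from scheduled visits will be used for summary tables". Unscheduled data are kept, but only for the subject listings.

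SAP 6.5 defines the treatment-emergent PCS table as "the number and percentage of subjects who had at least one PCS value on or after the first dose of study drug". Its denominator is the whole safety population, including subjects with no measurement after baseline. PCS values are also flagged in listings. SAP 6.5.3, 6.5.4 and 6.5.5 apply this count to laboratory tests, vital signs and ECG.

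For liver tests, SAP 6.5.3 says "Number and percentage of subjects with post-baseline abnormalities in liver tests will be summarized by treatment group", using the tiers of Table 3. The last row of that table pairs raised ALT or AST "at any treatment visit and any of the following AEs", within 14 days either way.

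None of these sections mentions unscheduled visits, either to admit them or to exclude them. Protocol 3.8.4.2 does not settle the question.

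Protocol 3.4 foresees testing off schedule. After a grade 3 finding the subject is promptly evaluated, "including repeat tests, evaluation of the baseline parameters, concomitant medications, etc". It adds: "The investigator may decide to evaluate or withdraw the subject from the study based on findings of lesser than grade 3 severity".

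**The concern.** A by-visit mean needs a nominal time point, so limiting it to scheduled visits is normal practice. A count of subjects who were ever abnormal needs no time point. Applied to that count, the rule removes results that bear directly on the question the table asks.

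The loss runs in one direction. An excluded result can only take a subject out of the numerator, or place the subject in a lower liver tier. The subject stays in the denominator, and so reads as a non-event.

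The PCS and Table 3 counts are the plan's by-arm summary of abnormal laboratory values, in a first study in patients with MTX as background. Listings hold the missing values but give no rate per arm. Two programmers could also read the SAP differently, one applying SAP 6 strictly and one taking SAP 6.5 at its word, and produce different tables.

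**Working it through.** The documents give no figure to reproduce here. The check is a comparison of texts, followed by one line of arithmetic.

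**Step 1. Is there an exception?** SAP 6 covers safety as well as efficacy. SAP 6.5 writes PCS-specific rules for the denominator and for the baseline, but none for visit type. SAP 6.5.3 to 6.5.5 and Protocol 3.8.4.2 add none. The general rule therefore governs.

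**Step 2. Which results are lost?**

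| Result at an unscheduled draw | Effect on the by-arm count under SAP 6 |
|---|---|
| Repeats a PCS value or liver tier already seen at a scheduled visit | None |
| First PCS value for that subject | Subject not counted |
| Higher Table 3 tier than at any scheduled visit | Subject counted in the lower tier only |
| First time a combined row (for example ALT with bilirubin) is met | Subject not counted in that row |

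The Early Termination Visit is specified in Protocol 3.4 with Visit 6 procedures. It is treated here as a planned visit, and is not part of the point.

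**Step 3. Would the AE tables catch it?** Protocol 3.6.1 asks for an abnormal result to be recorded as an AE if it comes with symptoms, leads to permanent discontinuation of study drug, or requires a change in concomitant therapy. Interruption of study drug is not on that list. However, Protocol 3.4 discusses interruption and restart under its adverse event heading, and Protocol 3.6.2 has an AE action category for it. Symptomatic cases should therefore reach the AE tables. An asymptomatic rise that prompts no such action may not.

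**Step 4. Size per subject.** Input: 50 subjects per arm (SAP 6.1), taken as the safety denominator.

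- Change in one arm's rate per uncounted subject: 1/50 = 0.020 = 2.0 percentage points.
- Hypothetical example: if five subjects in an arm were ever abnormal and one of them only at an unscheduled draw, the table would show 4/50 = 8.0% instead of 5/50 = 10.0%.

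The number of such subjects cannot be derived. It depends on how many unscheduled tests were done and on the PCS limits, which SAP 6.5 takes from an external standard.

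**The case against.** The strongest reply is that the scheduled-only rule is a legitimate choice. It gives every arm the same opportunities for testing. A count of all results does not: an arm with more unscheduled draws has more chances to record an abnormality. This stands, and it is why the scheduled-only count should be kept beside the fuller one.

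A second reply is that nothing is hidden, since all values are listed and PCS values are flagged. This also stands, but a listing is no substitute for a rate per arm.

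A third reply concerns the last row of Table 3, which may look the most exposed. It is the best protected, because raised ALT or AST with symptoms should be recorded as an AE. Its 14-day window also fits the schedule: with biochemistry on Days 14, 28, 56 and 84, no treatment day is more than 14 days from a planned test. A short rise could still be missing from that row, but it should appear among the AEs.

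Three stronger readings are tempting, and the documents do not support them.

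- A reader might infer that the SAP contradicts itself. It does not. The PCS definition sets a time window, not a visit type, and the treatment-visit wording in Table 3 can mean scheduled visits only.
- A reader might take the share of short episodes that fall between visits as the size of the loss. That share needs an assumed onset pattern and episode length. It also says nothing about how often an unscheduled result exists and is then excluded.
- A reader might take "The numerator is any PCS value in the treatment-emergent period if the baseline is normal or missing" to drop subjects whose baseline is out of range but not PCS. Read literally, such a baseline has no branch. The contrast with a PCS baseline in the same sentence suggests that not PCS was meant, and the effect cannot be known without the PCS limits.

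**Conclusion.** The point holds as a mismatch between a general rule and a particular kind of table. If SAP 6 is followed as written, the by-arm PCS and Table 3 counts can only equal or fall below the counts that use all post-dose results. The shortfall is 2.0 percentage points per uncounted subject in an arm of 50, and the number of such subjects is unknown.

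This rests on three things: SAP 6 applies wherever no exception is stated, the safety denominator is close to 50 per arm, and some unscheduled draws take place, as Protocol 3.4 expects. No test and no efficacy result is affected. AE tables and flagged listings recover part of the loss, especially for symptomatic subjects. The matter should be settled in the SAP before unblinding, but it does not threaten the study's main conclusion.

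**What to change.** - In SAP 6, limit the scheduled-visit rule, for safety, to by-visit summaries.
- In SAP 6.5 and 6.5.3, state that the PCS and Table 3 subject counts, including the last row of Table 3, use all results after the first dose, whether scheduled or unscheduled.
- Keep the scheduled-only count as a second line in the same tables.
- Show the number of unscheduled tests per arm, so that uneven ascertainment can be seen.
- Optional wording edit in SAP 6.5: describe the first baseline category as not PCS or missing, in place of normal or missing.

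The cost is a few sentences and minor programming. Reported rates may rise, and differences between arms in the all-results line may partly reflect how often subjects were tested. The second line and the test counts let a reader judge that.

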6.1 Sample Size

Approximately 250 eligible subjects (50 in each treatment group) are randomized into the DB treatment period of this study.

The primary efficacy evaluation will be to compare the ACR20 response rate between JTE-051 with placebo at EOT. From one study comparing mavrilimumab with placebo in combination with stable MTX, the ACR20 of mavrilimumab and placebo at Week 12 were 0.69 and 0.40, respectively. Assuming the ACR20 of at least one of the JTE-051 doses to be at least 0.30 above placebo, the following sample size per group will be needed to detect a statistical significant difference at the 5% level with about 80% power (using 2-sided Fisher's exact test):

Placebo ACR20	0.25	0.35	0.45
Sample size per group	47	48	47

About 50 randomized subjects per group would therefore give at least an 80% power for a range of placebo responses. The sample size calculation was carried out using the software SiZ 6.2 (Cytel Inc., 2013).

6.2 Subject Disposition Summary

Patient disposition will be summarized and tabulated by treatment group and in total. The number and percentage of patients in the randomized, safety, ITT, PP and PK populations will be tabulated. Discontinued patients and the reasons for discontinuation during the screening, DB treatment, or follow-up periods will be tabulated for the randomized population by treatment group and in total.

6.3 Demographics and Baseline Characteristics

Demographics and baseline characteristics as defined in Section 5.1 will be presented by treatment group with descriptive statistics for the randomized, safety, ITT and PP populations.

6.4 Efficacy Analysis

Analyses of primary and secondary efficacy parameters will be performed for both the ITT and PP populations, respectively.

For efficacy analyses, the DB treatment period is defined as the time period from the first dose of study drug to the last dose of study drug plus 4 days. The end of treatment (EOT) value is defined as the last value taken during the DB treatment period.

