- Generally, every effort should be made to ensure that all other permitted chronically-administered concomitant medications are taken by subjects at stable dose/route of administration for at least 4 weeks (28 days) prior to Day 1, unless a change in dose/route of administration is considered medically necessary.

[figure not shown]
General Medication-related Protocol Instructions:

[figure not shown]

- Generally, medication dose/route of administration changes or initiation of new medications during the conduct of the study is not recommended unless such actions are considered medically necessary, case when any appropriate action, according to the Investigator's judgment should be taken;
- All medications taken by the subject, including over-the-counter, herbal, traditional, ayurvedic compounds (whether permitted or excluded by the protocol) must be documented in the case report form (CRF);
- Contact the Medical Monitor with questions regarding prior/concomitant therapy.

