3.8. Statistical Methods

This section provides an abbreviated statistical analysis plan (SAP) for the efficacy and safety parameters. A formal SAP will be developed at a later time. Statistical issues not addressed in the present section may be developed in the formal SAP. The plans outlined in this section may be modified in the SAP; however, any major modifications of the primary endpoint definition and/or its analysis may also be reflected in a protocol amendment, as appropriate. Other deviations to the SAP will be discussed in the study report.

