3.8.3.2. Efficacy Data Analysis

For the purpose of efficacy analysis, the EOT value is defined as the last value taken during the DB treatment period after the first dose of study drug without any treatment intervention. For subjects who receive rescue treatment, the last value prior to the intervention will be defined as the EOT.

For the primary efficacy parameter (ACR20 at EOT), the Fisher's exact test will be used to compare each JTE-051 dose group with placebo. Furthermore, the exact Cochran-Armitage trend test²⁷ will be computed, using the ordinal score for treatment, e.g., score 1 for placebo, score 2 for the lowest JTE-051 dose, etc.

For dichotomous secondary efficacy parameters, similar analyses as the primary efficacy parameter will be used by time point, i.e., the Fisher's exact test for pairwise comparisons with placebo and the Cochran-Armitage test for trend.

[figure not shown]
For continuous efficacy parameter analysis with multiple time points, a mixed effect model will be employed. It includes fixed effects for treatment, time, treatment by time interaction, the stratification factors and the appropriate baseline, and subject as the random effect. The appropriate baseline will be the parameter from which the efficacy parameter is derived, e.g., SDAI at Week 0 for the analysis of change from baseline in SDAI. The treatment effect of each JTE-051 dose group relative to placebo at the same time point will be estimated. A linear trend test at each time point will be computed using appropriate linear contrast.

[REDACTED]

All analyses will be performed two-sided at the 5% significance level. No formal multiple comparison adjustment will be made, therefore results should be interpreted with the multiplicity in mind. The estimated treatment effect (relative to placebo) from the model, along with a two-sided 95% CI and p-value, will be tabulated where appropriate. The Newcombe's CI of the rate difference²⁸ between JTE-051 dose and placebo will be computed when performing the Fisher's exact test. Graphical presentations of the treatment profile may be depicted. Sensitivity analysis, model fit assessment may be conducted and data transformation may be employed if appropriate.

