4.4 Per Protocol (PP) Population

The Per Protocol (PP) population is a subset of the ITT population in which subjects do not incur any of the major protocol deviations below.

Major protocol deviation criteria:

1. Dosing compliance not in 80-120% (based on actual dosing period)
2. Subject's last dose not between Days 68-100
3. Subject did not take 272-400 tablets in total
4. >4 days between last dose and last non-follow-up efficacy assessment
5. Not meeting Inclusion Criterion #3 or #4
6. Not meeting Exclusion Criterion #1, #2 or #28
7. Subject took "key" prohibited concomitant medications or had unstable background therapy that could potentially affect efficacy results/interpretation
8. Subject took incorrect study medication, e.g. due to incorrect drug dispense
9. Significant procedural deviations/non-compliance that could potentially affect efficacy results/interpretation

A pre-analysis meeting will take place after all data have been entered into the database and cleaned, but before the release of the randomization code, to identify the PP population. The decisions made to select the PP population will be documented.

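### The SAP's end-of-treatment value drops the protocol's intervention and rescue conditions, so the primary endpoint has two definitions

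*SAP*

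**What the plan says.** Protocol 3.8.3.2 sets two conditions on the EOT value. It must be the "last value taken during the DB treatment period after the first dose of study drug without any treatment intervention". The next sentence deals with rescue: "For subjects who receive rescue treatment, the last value prior to the intervention will be defined as the EOT".

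SAP 6.4 gives a self-contained definition. It first sets the double-blind window for efficacy, which opens with the first dose and closes 4 days after the final one. Then: "The end of treatment (EOT) value is defined as the last value taken during the DB treatment period". It contains no intervention condition and no rescue condition.

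EOT is the time point of the primary endpoint in both documents (Protocol 3.8.3.1, SAP 5.2.1). SAP 5.2.2 also adds EOT as an evaluation time for the secondary parameters, so the difference reaches beyond ACR20.

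Protocol 3.8 allows the SAP to modify the plan, and adds that "any major modifications of the primary endpoint definition and/or its analysis may also be reflected in a protocol amendment, as appropriate".

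**The concern.** The two definitions can give the same subject different ACR20 outcomes. If someone who has not responded receives additional anti-rheumatic treatment and then improves, the SAP credits that improvement to the randomised arm in the primary ITT comparison. The protocol does not.

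The direction of the error depends on where such subjects fall. An excess on placebo would mask a real effect, an excess on one active dose would flatter that dose, and equal numbers would change little. With both definitions on file and no explanation, the result could also be argued either way once the treatment codes are known.

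**Working it through.** **1. The two rules applied to one subject.** Table 1 schedules efficacy visits at Weeks 2, 4, 8 and 12.

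| Case | Protocol 3.8.3.2 | SAP 6.4 |
|---|---|---|
| Rescued between Weeks 8 and 12, stays on study drug | Week 8 value | Week 12 value |
| Stops study drug, changes therapy, is assessed within 4 days of last dose | last value before the change | value after the change |
| No intervention | last double-blind value | last value up to last dose plus 4 days |

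**2. Does other visible SAP text restore the conditions?** No.
- SAP 5.2.1 and 6.4.1 name ACR20 at EOT without defining EOT.
- SAP 4.4, criterion 7, removes subjects who took key "prohibited concomitant medications or had unstable background therapy that could potentially affect efficacy results/interpretation". This changes membership of the per-protocol set and leaves the ITT value as it was.
- SAP 6.4.10 imputes non-response only after withdrawal for treatment-related adverse events, and only in analyses over multiple time points.

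**3. Can such subjects occur?** Protocol 3.5.4.1 prohibits many anti-rheumatic changes. Protocol 3.4 and 3.5.2 ask that leavers be assessed before their therapy changes, but as an effort to be made or where possible. The general medication instructions leave a route open: "initiation of new medications during the conduct of the study is not recommended unless such actions are considered medically necessary".

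**4. The plan's own sample size.** Inputs from SAP 6.1: two-sided Fisher's exact test at 0.05, difference 0.30, placebo ACR20 of 0.25, 0.35 and 0.45. Power is the sum, over all pairs of responder counts (a, b), of Bin(a; n, p_active) × Bin(b; n, p_placebo) for the tables with Fisher p ≤ 0.05.
- At the stated 47, 48 and 47 per group: 79.9% in each case, so the plan's figures reproduce.
- At the planned 50 per group: 83.5%, 82.8% and 83.5%.

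**5. Illustration of what is at stake.** The documents give no rescue rate, so the shifts are assumed. One subject in an arm of 50 is 1/50 = 2 percentage points.

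True difference 0.30, n = 50 per arm, power:

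| Expected extra false responders | Placebo 0.25 | 0.35 | 0.45 |
|---|---|---|---|
| none | 0.835 | 0.828 | 0.835 |
| 1, placebo only | 0.774 | 0.768 | 0.778 |
| 2, placebo only | 0.703 | 0.700 | 0.711 |
| 1 in each arm | 0.832 | 0.828 | 0.840 |
| 2 in each arm | 0.830 | 0.828 | 0.848 |
| 3 in each arm | 0.828 | 0.830 | 0.859 |

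No true effect, excess on one active dose, probability of a significant result favouring that dose:

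| Expected extra false responders | Placebo 0.25 | 0.35 | 0.45 |
|---|---|---|---|
| none | 0.0151 | 0.0152 | 0.0172 |
| 1 | 0.0263 | 0.0252 | 0.0279 |
| 2 | 0.0432 | 0.0403 | 0.0437 |

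The same illustration as rescue rates, assuming all rescued subjects were non-responders beforehand and half then reach ACR20:
- 5% of placebo and no active subjects rescued: the difference becomes 0.30 − 0.05 × 0.5 = 0.275, power 0.75-0.76.
- 20% of placebo and 10% of active: 0.30 − (0.20 − 0.10) × 0.5 = 0.25, power 0.66-0.71.
- 5% in both arms: the difference stays 0.30, power 0.83-0.84.

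**6. One subject at the boundary.** 28/50 against 17/50 gives p = 0.044. Moving one placebo subject (28 against 18) gives p = 0.070; moving one active subject (27 against 17) gives p = 0.069.

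**The case against.** The strongest reply is that the dropped clause may have little to act on. Rescue treatment is mentioned once in the visible protocol, no visible passage provides for it, and anti-rheumatic changes are tightly restricted. Rescue with continued study drug would be unusual. That stands as a limit on the size of the problem. It does not remove the conflict: medically necessary changes are allowed, and the protocol itself thought a rescue rule was needed.

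The SAP may modify the protocol, and it states one definition, so the difference is not in itself a breach. That is right. The defect is that a changed primary-endpoint definition is neither flagged nor explained.

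SAP 6.4 makes the per-protocol analysis of the primary endpoint unconditional, whereas Protocol 3.8.3 required it only if 20% or more of ITT subjects were excluded. With criterion 7, this could help expose a material artefact. It does not correct the ITT value. The SAP's window is also tighter in one respect, since it excludes values taken more than 4 days after the last dose.

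The numbers are hypothetical and assume an imbalance between arms. That is so. With no true effect, one extra active responder only brings the rate to about the nominal 2.5% per direction, because Fisher's test starts well below it. The single-table examples show how fragile any borderline result is and are not specific to this defect.

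Finally, some numbered subsections are not visible (SAP 5.2.3-5.2.4 and 6.4.5-6.4.6; Protocol 3.5.5). A rescue definition or related analysis could sit there.

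**Conclusion.** The concern holds. The two documents define the primary EOT value differently, and nothing in the visible SAP restores the protocol's conditions for the ITT analysis. Confidence in the difference of wording is high; how many subjects it touches is unknown and may be few or none.

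The practical size rests on three assumptions: that some subjects are treated during the double-blind window, that they respond only afterwards, and that they are unevenly spread across arms. Under those assumptions, an expected one-subject excess on placebo already takes power below the stated 80%. With even spread the effect is negligible. The planned sample size itself is sound. This should be fixed before unblinding; it is a correction to the plan's text and does not call the design into question.

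**What to change.** - **Reconcile the definitions.** In SAP 6.4, restore the protocol's conditions (no intervention; last value before rescue). Alternatively, state and justify the new definition and amend Protocol 3.8.3.2 to match.
- **Define the terms for analysis.** Say which recorded medications count as a treatment intervention or as rescue, since neither document visibly does so. This concerns data derivation only; no rule on when rescue may be given is proposed.
- **Identify affected subjects blind.** Use the concomitant-medication data at the pre-analysis meeting that SAP 4.4 already schedules before release of the randomization code, and report the number by arm.
- **Optional.** Add one sensitivity analysis counting these subjects as ACR20 non-responders at EOT. Reconciliation does not depend on it.

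The cost is a few lines of SAP wording (plus a protocol amendment if the new definition is kept), a short blinded review, one derivation flag and, if wanted, one extra table. Restoring the conditions may slightly lower observed response rates.
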